Once enrolled, participants will complete HabitWorks daily on their smart phones in a quiet room while attending the partial hospital, three times per week at home for 1-month following discharge, and as desired during the final 2 months. Sessions during the follow-up period will include approximately 75 trials and thus will only require 5 minutes to complete.

During the 1-month post-acute period, participants will complete assessments of symptoms (PHQ-9 and GAD-7) as often as desired, including optional once weekly check-ins and daily assessment of affect (see EMA description in Measures). These surveys will be administered

via Metricwire. The Metricwire app was designed to protect participants' privacy, confidentiality, and data security. Only research personnel will have access to study information. Data collected by the Metricwire app is encrypted, and downloaded by the researcher to the local research server in a de-identified format (i.e., subject ID number). The local research server is only accessible by study staff. Study staff will provide orientation to the app and answer any questions regarding the assessments and data collected.

Treatment phase	Location	Frequency of sessions	Session duration
Acute (1 to 14 days)	Hospital	Daily to augment CBT-based hospital treatment	10 min
Transition (1-month)	Home	3x per week to transition from intensive hospital to outpatient care	5 min
Long-Term (2 mo)	Home	Sessions completed as desired by individual	5 min

Following Long-Term phase (post 3months from discharge) EPIC Research trained study staff will check every patients EMR, whether or not they completed the 3month assessment, for data on rehospitalization or ER visits and the reason why. This data will then be de-identified and kept in partners secure storage (Dropbox).

**Retention.** Post-discharge, staff will monitor participants' progress with the HabitWorks app daily and will call participants who have not completed any sessions in the past week. The purpose of these phone calls will be to help identify barriers and brainstorm potential solutions. To increase retention, we will: a) obtain contact information of individuals who will always know how to reach participants; b) pay participants for assessments; and c) provide transportation if needed, flexible scheduling for the assessments, and in rare individual cases conduct interviews via telephone.

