**HabitWorks**

Participants assigned to HabitWorks will complete the same procedures as outlined in the Open Trial. Specifically, participants will complete a task designed to improve interpretation biases. During each session, participants complete the previously validated word-sentence association paradigm (~10 min). The task presents ambiguous sentences (“You failed an exam”) and provides positive feedback (“you are correct!”) when participants endorse benign interpretations/attributions (“difficult test”) and negative feedback (“you are incorrect!”) for negative interpretations/attributions (“stupid”). Sessions during the transition phase are shorter (~5 min).

Once enrolled, participants will be asked to complete HabitWorks daily on their smart phones in a quiet room while attending the partial hospital, at least three times per week at home for 1-month following discharge, and as desired during the final 2 months. During the 1-month post-acute period, participants may complete assessments of symptoms (PHQ-9 and GAD-7) as often as desired, including optional once weekly check-ins for the study. For people in the HabitWorks condition, these surveys are administered via the HabitWorks app.

During the 1-month post-discharge period, participants will also complete daily assessment of affect (see EMA description in Measures). These surveys will be administered via Metricwire. The HabitWorks and Metricwire app was designed to protect participants' privacy, confidentiality, and data security. Only research personnel will have access to study information. Data collected by the Metricwire app is encrypted, and downloaded by the researcher to the local research server in a de-identified format (i.e., subject ID number). The local research server is only accessible by study staff. Study staff will provide orientation to the app and answer any questions regarding the assessments and data collected.

HabitWorks Treatment phase	Location	Frequency of sessions	Duration
---------------------------------------	-----------------	------------------------------	-----------------

Acute (1 to 14 days)	Hospital	Daily to augment CBT-based hospital treatment	10 min
Transition (1-month)	Home	3x per week to transition from intensive hospital to outpatient care, 4x daily affect surveys, weekly symptom monitoring survey	15 min/day

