### Phase 2: Open Trial

The primary aims of this treatment development project are to develop: a) HabitWorks, b) procedures for hospital augmentation and bridge to outpatient care, and c) procedures for a subsequent RCT. First, we will analyze qualitative data obtained from post-treatment interviews and exit questionnaire. The PI will content analyze audio recordings using a rapid coding technique. Audio recordings will then be transcribed verbatim and analyzed with more conventional analytic methods. Using the constant comparison method from grounded theory transcripts will be read for emerging themes. After independently categorizing thematic clusters, the scientific team will create a coding scheme to organize data, prepare a written report detailing the emerging themes, and discuss results with the advisory board.

We will compare outcomes to a **priori target outcomes** (see Table) after each iteration of the open trial. We will calculate descriptive statistics (e.g., mean, frequencies) to evaluate whether the target outcome was met. When the target is not met, this will prompt a discussion with the team and advisory board about potential modifications. We will calculate effect size estimates to characterize pre-post differences (open trial) and the associated 95% CIs, to understand the precision, or lack thereof, of our estimates.

Target Outcomes	
Target Engagement:	75% of HabitWorks group moves into normal range  of interpretation bias (Benign endorsement = 70%; Negative endorsement = 30%) on the WSAP and on the Scenario Recognition Task ( Similarity rating (1 to 4) for target sentences: benign = 2.3; negative = 1.9).
Treatment Credibility & Expectancy:	Average = 5 (moderate credibility or 50% expectancy)
Retention:	75% of participants complete the 3 month-assessment 75% of participants complete HabitWorks daily during acute treatment 50% of participants complete HabitWorks 3x week in transition phase
Satisfaction:	Average rating 5 or above (on a 1 to 7 scale) on the Exit Questionnaire
Treatment response:	50% of HabitWorks group responds to treatment (“much or very much improved” on CGIS) and 20% reduction in functional impairment in HabitWorks group with a clinically meaningful between group effect size of $d = .40$

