**Case series:** We will report results from 4 participants from the Phase 2 open trial and the Phase 3 randomized controlled trial in a case series format. We will report data on app usage, clinical outcomes, and app feedback collected throughout the project. In all 4 participant case reports, we will remove any identifiable information, and will report limited demographic information (e.g., age range, gender, race, and ethnicity).

**EMA data.** We will pilot the use of EMA methods and anticipate following a similar analytic strategy as prior EMA work. In brief, we will examine change in affect using repeated measures ANOVA. We hypothesize that individuals who complete the WSAP just prior to the random EMA PANAS-X assessment will report an increase positive affect and a decrease in negative affect from the prior EMA assessment. We will primarily rely on Latent Growth Models (LGM) due to our interest, and hypotheses, related to HabitWorks administration and change in interpretation events. LGM provides a flexible, powerful, and easily interpreted statistical approach to examine affective and cognitive change modeled around a discrete event. We first construct models for negative and positive affect; these models will initially be specified as parallel growth processes to account for shared variance, but will be tested individually if a parallel growth model cannot be fit. We will estimate intercept (i.e. mean) and slope (i.e. linear

rate of change over time) for each of these constructs using the anchor event (i.e. HabitWorks session) and 1-2 EMA assessments before and after, providing 3-5 time points to model change. Should linear slope poorly describe the data, we will investigate nonlinear slope or specify piecewise, discontinuous, linear growth processes. We first fit unconditional models to determine the optimal change trajectory for each outcome. Once an optimal growth trajectory has been identified, we regress growth parameters (i.e. intercept and slope) on changes in WSAP responses to examine the association of intercept and slope of interpretation bias outcome variables with affect and symptoms.

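### The EMA growth models are built on windows around single HabitWorks sessions, about 12–13 of them scheduled per participant, but the SAP names no participant level

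*SAP*

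**What the plan says.** The EMA paragraph of the SAP (Phase 2: Open Trial) relies mainly on latent growth models of positive and negative affect. It justifies them this way: "LGM provides a flexible, powerful, and easily interpreted statistical approach to examine affective and cognitive change modeled around a discrete event". Intercept and slope are estimated "using the anchor event (i.e. HabitWorks session) and 1-2 EMA assessments before and after, providing 3-5 time points to model change". Once a trajectory has been chosen, "we regress growth parameters (i.e. intercept and slope) on changes in WSAP responses". The same paragraph states that "we will examine change in affect using repeated measures ANOVA", and that the team will "anticipate following a similar analytic strategy as prior EMA work". The Phase 3 section of the SAP says that similar EMA analyses will be run in the RCT.

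The Protocol sets the number of anchor events. Open-trial participants do HabitWorks "three times per week at home for 1-month following discharge"; RCT participants in the HabitWorks arm are asked to do it "at least three times per week at home for 1-month following discharge". The affect surveys run four times a day through that month (Protocol, Ecological Momentary Assessment). The SAP's adherence target is modest: "50% of participants complete HabitWorks 3x week in transition phase".

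The SAP plans for failure of the parallel-process model and for nonlinear or piecewise slopes. It does not state the unit of analysis, how several sessions from one person are combined or selected, or any participant random effect or clustered standard error.

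**The concern.** A trajectory of three to five points around a session belongs to that session, and one participant supplies many of them. Windows from the same person share that person's usual mood and, to some degree, their usual response to a session. If every window enters as an independent case, two things go wrong.

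- Standard errors come out too small. This affects the mean slope when people differ in their typical response, and the regression on WSAP change when both affect and WSAP change differ stably between people.
- The coefficient on WSAP change mixes two associations. One is that people who show more change also feel better. The other is that a person feels better after sessions with more change. Only the second supports a session effect, and it is the one behind the SAP's hypothesis that completing the task just before a survey improves affect.

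The project exists to supply pilot data for a larger trial. A difference between people that is read as an effect of a session would be carried into that trial's rationale.

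**Working it through.** **Inputs from the documents**
- Window: 1 anchor plus 1 or 2 surveys on each side, so 1 + 2×1 = 3 and 1 + 2×2 = 5 points. This agrees with the SAP.
- Sessions per person: 3 per week gives 12 in 28 days, 3 × 30/7 = 12.9 in 30 days and 3 × 31/7 = 13.3 in 31 days. The documents do not state a total.
- HabitWorks participants: 16 in the open trial. For the RCT the Protocol gives 64 in Subject Selection and 84 in Study Procedures, hence about 32 or 42 if allocation is equal (an assumption).

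**Assumptions.** The documents give no ICC and no test level for these models, so there is no stated error rate or precision to reproduce. I assume two-sided 5% and four sets of person-level ICCs for affect intercept (ρ_y), WSAP change (ρ_x) and slope (ρ_s).

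**Formulas**, for m sessions per person pooled as independent:
- Mean slope: DE = 1 + (m − 1)ρ_s.
- Intercept on WSAP change: DE ≈ 1 + (m − 1)ρ_y ρ_x.
- The standard error is understated by a factor √DE.
- Actual rejection rate under no effect = 2[1 − Φ(1.96/√DE)].

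Example at m = 13, ρ_y = ρ_x = .5: DE = 1 + 12 × .25 = 4, √DE = 2, and 2[1 − Φ(0.98)] = 33%.

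| ρ_y, ρ_x, ρ_s | m | Intercept on WSAP: DE, rejection | Mean slope: DE, rejection |
|---|---|---|---|
| .3, .1, .02 | 13 | 1.36, 9% | 1.24, 8% |
| .4, .2, .05 | 13 | 1.96, 16% | 1.60, 12% |
| .5, .3, .10 | 13 | 2.80, 24% | 2.20, 19% |
| .5, .5, .10 | 13 | 4.00, 33% | 2.20, 19% |
| .3, .1, .02 | 6 | 1.15, 7% | 1.10, 6% |
| .5, .5, .10 | 6 | 2.25, 19% | 1.50, 11% |

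**Simulation.** Simulating the same settings under no effect gives slightly wider ranges. At 13 sessions they are about 9–35% for intercept on WSAP change and 7–20% for the mean slope; at 6 sessions, about 6–21% and 6–13%.

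**Interval width.** At 13 sessions the 95% interval should be √1.36 = 1.17 to √4 = 2.00 times as wide for the WSAP coefficient, and √1.24 = 1.11 to √2.20 = 1.48 times as wide for the mean slope.

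**When the problem vanishes.** With ρ_x = 0 the regression DE is 1, and simulated rejection is 4.0–6.2%. The mean-slope test stays inflated as long as ρ_s is above zero.

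**Does accounting for participant repair it?** Testing the mean on participant averages gives 4.2–5.5% in simulation with 16, 32 and 42 participants. Ordinary participant-clustered standard errors in the regression improve matters but stay somewhat liberal: 5.6–9.4% over the same sample sizes, with outcome ICCs of .05–.30 and ρ_x of .5 or 1.

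**The case against.** The strongest reply is that silence is not pooling. A reader might infer that the SAP treats sessions as independent, so that its standard errors are too small and its false-positive rate is above 5%. The documents do not support that as a statement of fact. The SAP never names the unit. It words its hypothesis in terms of individuals, it defers to a prior EMA strategy that the documents do not reproduce, and a multilevel model or one averaged window per person would fit the text. It also sets no 5% level for these analyses.

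Other points against also have force. Thirteen is the schedule, not the expected yield: the adherence target is 50% of participants at that rate, and a usable window also needs answered surveys on both sides. All the ICCs are assumed. Repeated-measures ANOVA does model within-subject dependence.

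Some of the concern survives all of this. With several windows per person the analyst must pool, select, average or add a level. Pooling is the only choice that needs no step beyond what is written; each of the others needs a rule that the SAP lacks. The reference to earlier work is tentative and does not supply one. Fewer sessions shrink the inflation but do not remove it. The ANOVA has no stated error term, and session counts will be unequal across people. Even with correct standard errors, the undivided WSAP predictor would still mix between-person and within-person association.

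A reader might also infer that the trial's main conclusions are at risk. They are not. The co-primary clinical outcomes are the CGIS and WSAS, the SAP describes the EMA work as a pilot, and no EMA result appears among its target outcomes or in its power calculation.

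**Conclusion.** The concern holds in conditional form. The growth models are specified at the level of a session window, participants supply many windows, and the plan provides no participant level. Whether the error rates shown above arise depends on two things that the documents leave open: that windows are pooled without adjustment, and that affect, slope or WSAP change has person-level variance of the assumed size. If the predictor varies only within persons, the WSAP regression is unaffected. The intervals are too narrow under the same conditions as the tests are liberal, so the point matters even if the EMA results are reported only as estimates with 95% intervals. It is worth correcting before the EMA data are analysed, at the priority that an exploratory pilot analysis deserves.

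**What to change.** Amend the EMA paragraph of the SAP, for both phases, as follows.

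1. State that EMA assessments are nested in sessions and sessions in participants.
2. Fit the growth model with a participant level. Alternatively, use participant-clustered standard errors with a small-sample correction, because with only 16–42 participants the uncorrected version stays liberal.
3. Split WSAP change into each participant's mean and the deviation of each session from that mean. Base the session-effect claim on the within-person coefficient.
4. Where the repeated-measures ANOVA would use several, unequally many sessions per person, replace it with a mixed model with a participant random effect.

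This needs no new data, only SAP wording and some added modelling work. Intervals will be wider. A three-level parallel-process model may not converge with this few participants, so name the clustered-error version in advance as the fallback.

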Demog. Form, CEQ	X				
PHQ-9; GAD-7	X	X	X	X	X
Q-LES-Q, BHS, CFI, MPS, GSE	X		X	X	X
Exit Questionnaire				X	
WSAP	X	X	X	X	X
Scenario Recognition Task				X	
EMA PANAS	X	X	X	X	X
CSSRS- Self Report	X			X	X
System Usability Scale- HW condition				X	
TWEETS- HW condition				X	

The Scenario recognition task is the most widely used assessment of interpretation bias in CBM- and will ensure that effects are not solely attributable to practice or method effects. In brief, participants first read 10 ambiguous scenarios and a comprehension question to ensure they actually read the scenario. In the second phase, participants read the title of the ambiguous scenario followed by four versions of the final sentence presented in a random order. Sentences represent a) a possible positive interpretation, b) a possible negative interpretation, c) a positive foil, and d) a negative foil.

Participants rate each sentence for its similarity in meaning to the original story using a 4-point scale ranging from 1 (very different in meaning) to 4 (very similar in meaning). We will calculate the average similarity rating for negative and positive interpretations.

Co-primary clinical outcomes will include stake-holder relevant measures of global improvement and functioning. The PI will train study staff to administer these brief scales and will monitor reliability using established procedures at the BHP.

Clinician-administered Clinical Global Improvement Scale (CGIS) to assess global improvement.

Clinician-rated 5-item Work and Social Adjustment Scale (WSAS) to assess interference caused by the patient's symptoms in the domains of work, home management, leisure, and family relationships.

Other self-report measures will include:

Credibility Expectancy Questionnaire to assess patients' beliefs about the treatment expectancy (affectively based) and treatment rationale credibility (cognitively based).

Exit Questionnaire to assess patients' satisfaction with the treatment provided.

Beck Hopelessness Scale (BHS) to assess negative attitudes about the future.

Cognitive Flexibility Inventory: The Cognitive Flexibility Inventory is a measure of mental flexibility and assesses the degree to which individuals are able to replace maladaptive thoughts with adaptive ones and maintain a balanced mindset.

15-Item Multidimensional Perfectionism Scale (short form): The MPS is a widely used self-report measure of perfectionism.

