**Power analysis.** One goal of the current project is to determine the recruitment rate at our site, and to compare it to the rate needed for an adequately powered RCT (i.e., 4 individuals per month = 200 participants over 50 months (estimated recruitment duration of a subsequently proposed RCT)). Our primary hypothesis for the subsequent RCT is that HabitWorks will be superior to control on our primary outcomes. We determined that a clinically significant difference for a low-intensity, augmentation treatment is an effect size of  $d = .40$ , which corresponds to a post-treatment between-group difference of 2.8 points on the WSAS. We conducted preliminary power analyses using these numbers and a 15% dropout rate (based on our pilot studies). We estimated that a sample size of 200 would give us >80% power to detect a group difference of  $d = .40$ . This effect appears feasible, given that our pilot RCT resulted in a between-group effect size of  $d = .63$  on a measure of well-being.

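### The >80% power for 200 patients and the 4-per-month benchmark are worked out for one WSAS effect, while the hypothesis they support names two co-primary outcomes and no success rule

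*SAP*

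**What the plan says.** The power paragraph (SAP, VI. Biostatistical Analyses, Phase 2: Open Trial) concerns a later RCT. It gives the hypothesis in the plural: "Our primary hypothesis for the subsequent RCT is that HabitWorks will be superior to control on our primary outcomes".

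The Protocol identifies the outcomes in Measures (Section V): "Co-primary clinical outcomes will include stake-holder relevant measures of global improvement and functioning". It then lists the clinician-administered CGIS and the clinician-rated WSAS. The pilot-study summary in the Protocol's Background names the same two as primary.

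The power calculation has one effect size. It is d = .40, "which corresponds to a post-treatment between-group difference of 2.8 points on the WSAS". With a 15% dropout allowance, the SAP says that "a sample size of 200 would give us >80% power to detect a group difference of" that size. The same paragraph sets the recruitment rate that this project will be compared with: 4 per month for 50 months, which makes 200.

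The paragraph gives nothing for CGIS: no effect size, control rate or form of analysis. It also gives no alpha, sidedness, test, correlation or multiplicity rule, and does not say whether one or both outcomes must succeed. CGIS is scored as a response rate only in the SAP's Target Outcomes table, where the goal is that "50% of HabitWorks group responds to treatment".

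**The concern.** A power figure is tied to a success criterion. A single d = .40 with 200 analysed gives barely more than 80%, so there is almost no slack. If a second outcome must also succeed, power generally falls below the stated level. If either outcome suffices, some multiplicity control is needed and the power is different again. The printed >80% therefore cannot be attached to the hypothesis as worded.

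The practical stake is the benchmark. One aim of the project is to compare the site's recruitment with the rate that an adequately powered RCT needs. If that rate is derived for a narrower hypothesis than the one stated, a site recruiting 4 per month could be judged adequate for a trial that needs more.

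**Working it through.** **Inputs from the documents.** N = 200, d = .40 (2.8 WSAS points, so the implied SD is 2.8/0.40 = 7.0), dropout 15% (200 × 0.85 = 170 analysed), 50 months of recruitment, two co-primaries, and a CGIS response target of 50% in HabitWorks.

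**Assumptions, because the documents are silent.** 1:1 allocation, two-sided 5%, unadjusted two-group comparison, correlation between the two test statistics from 0 to 0.8, control CGIS response from 25% to 40%.

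**Step 1: the plan's own figure, one continuous outcome.** Power = Φ(d·√(n/2) − 1.96), with n per arm.
- n = 100: 0.40 × √50 = 2.828; 2.828 − 1.960 = 0.868; power 80.7% (t-test 80.4%). This reproduces >80%, but with no dropout.
- n = 85: 0.40 × √42.5 = 2.608; 2.608 − 1.960 = 0.648; power 74.1% (t-test 73.7%).
- With 85 per arm, >80% returns under a one-sided 5% test (83.2%) or with baseline adjustment at a correlation of 0.4 (81.2%). At 0.3 it is 78.0%. The SAP states neither device.

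**Step 2: both outcomes must succeed, both continuous with d = .40.** Joint power is the bivariate normal probability Φ₂(z₁, z₂; ρ), where each z is the normal quantile of the single-outcome power. At ρ = 0 it is the square: 0.807² = 0.652 and 0.741² = 0.550.

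| Analysed | ρ = 0 | ρ = 0.5 | ρ = 0.8 |
|---|---|---|---|
| 200 | 65% | 70% | 74% |
| 170 | 55% | 61% | 66% |

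**Step 3: both must succeed, CGIS analysed as response with 50% in HabitWorks.** CGIS power = Φ[(|p₁ − p₂| − 1.96·√(2p̄(1−p̄)/n)) / √((p₁(1−p₁) + p₂(1−p₂))/n)]. Example with n = 100 and 50% against 40%: (0.100 − 0.138)/0.070 = −0.54, so 29%. The joint figures combine this with the WSAS power over ρ = 0 to 0.8.

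| Control response | CGIS alone, 200 analysed | Both, 200 analysed | Both, 170 analysed |
|---|---|---|---|
| 25% | 96% | 78–80% | 69–74% |
| 30% | 83% | 67–75% | 57–67% |
| 34.5% | 60% | 49–58% | 40–51% |
| 40% | 29% | 24–30% | 19–26% |

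The 34.5% row is the latent-normal equivalent of d = .40 against 50%: Φ(−0.40) = 0.345. Pooled and unpooled variances differ by about a point or less in these joint ranges.

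**Step 4: either outcome suffices, Bonferroni at 2.5% each, both continuous with d = .40.** Single-test power is 72.1% (200) or 64.3% (170). Power for at least one = 2 × single − joint.
- 200 analysed: 92% at ρ = 0, down to 81% at ρ = 0.8.
- 170 analysed: 87% down to 74%.

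**Step 5: benchmark in enrolled patients.** Enrolled = analysed/0.85; monthly rate = enrolled/50.
- One continuous outcome, 80% power: 198 analysed; 198/0.85 = 233 enrolled; 233/50 = 4.66 per month.
- Both continuous outcomes, 80% joint power: 258 analysed at ρ = 0 and 230 at ρ = 0.8; 258/0.85 = 304 and 230/0.85 = 271 enrolled; 6.1 and 5.4 per month.

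**The case against.** Four points on the other side carry weight.

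1. **The SAP never says that both outcomes must succeed.** This is correct. Superiority on outcomes described as co-primary reads most naturally as both, and a reader might take that as the stated rule. It is not stated. Under the either-outcome rule of step 4, with all 200 analysed, the >80% holds. After dropout it holds only at the lower correlations.
2. **Response scoring of CGIS belongs to the pilot.** This is also correct. The 50% is a descriptive target for the HabitWorks arm, and d = .40 in that table row most plainly attaches to functional impairment. A reader might infer that the later trial will test CGIS response and that joint power is near one half. The documents give neither that analysis nor a control rate for this definition, so only a range can be shown. At 25% control response with 200 analysed, the shortfall nearly disappears. The two-continuous calculation in step 2 does not rely on response scoring.
3. **A one-sided or baseline-adjusted analysis could recover power.** It could, but neither is stated. A one-sided 5% test with 170 analysed gives 69–77% on two continuous outcomes, still under 80%.
4. **The calculation is preliminary and belongs to a later trial.** This stands and limits the consequence. The present RCT is not sized by it and plans only between-group effect sizes with 95% CIs. No go/no-go decision hangs on the 4-per-month rate. The project does, however, set out to compare itself with that rate.

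**Conclusion.** The point holds as a mismatch between a hypothesis on two primary outcomes and a power figure and benchmark built on one WSAS effect. That much is in the text and needs no assumption.

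The size of the shortfall depends on rules the plan leaves open: success rule, alpha, sidedness, test, correlation, CGIS analysis and control rate. Under the natural but unstated both-outcomes reading, with two continuous outcomes, power is 65–74% with 200 analysed and 55–66% with 170. With CGIS as response and 200 analysed, it runs from 78–80% (control 25%) to 24–30% (control 40%). Under an either-outcome Bonferroni rule with two continuous outcomes, it is 81–92% or 74–87%.

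Two stronger conclusions should not be drawn. The SAP's arithmetic is not shown to be wrong: 200/50 is 4, and one outcome with 200 analysed gives just over 80%. Nor is the current RCT shown to be too small, because it makes no power claim. The point merits correction because the fix is cheap and the benchmark is one of the project's outputs.

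**What to change.** Revise the SAP's power paragraph as follows.

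- Label the power as that for one continuous outcome (WSAS), with the 15% dropout applied. At two-sided 5% and unadjusted, that is about 74%. If >80% is to stand, state the one-sided or baseline-adjusted test that delivers it. Relabelling >80% as the WSAS figure without this would leave it in conflict with the stated dropout.
- State the success rule for the later RCT: both outcomes, or either with a named multiplicity adjustment. State alpha and sidedness.
- State how CGIS will be analysed and, if as response, the assumed control rate.
- Give the matching power over a range of correlations and control rates. The pilot's own data can later narrow these.
- Restate the recruitment benchmark in enrolled patients. For 80% joint power on two continuous outcomes with 15% dropout, it is about 271–304 enrolled, or 5.4–6.1 per month over 50 months.

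The cost is a few sentences and a short calculation. The pilot's size and procedures do not change. The drawback for the sponsor is a less favourable stated power and a higher recruitment benchmark, unless the chosen rule and test support the present figures.

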**Pilot study in a partial hospital.** Participants ( $n = 65$ ) met criteria for a range of diagnoses, and 70% met criteria for moderate or high suicide risk on the clinician-administered MINI (specific suicide plans and suicidal gestures and attempts). The average number of prior hospitalizations was 2 (range 0 to 20). This pilot study did not include a measure of functional impairment; however, a prior sample from the same partial hospital reported significant disability on the Sheehan Disability Scale ( $M = 7$  (out of 10) for each domain).

**Does interpretation bias matter in a hospital population?** Almost all prior studies of interpretation bias have compared a healthy control group to a psychopathology group; thus, we first examined the clinical relevance of interpretation bias *within* a SMI sample. Even in a restricted range of high symptom severity in our partial hospital, robust associations were found with interpretation bias. Controlling for baseline symptom severity, **patients who endorsed fewer benign interpretations at admission were less likely to respond to treatment** (defined as "very much improved" on the self-reported Clinical Global Improvement Scale), and this model **accounted for 28% of the variance in treatment response**. Interpretation bias upon admission also prospectively predicted **suicidal ideation at discharge** better than any other demographic or clinical variable.

**Randomized Controlled Trial.** Patients were randomly assigned to CBM-I or a neutral control condition. All individuals received treatment as usual at the partial hospital. Patients completed the 10-minute task each day they attended the partial hospital on a laptop computer.

Assessments of interpretation bias and symptoms occurred upon admission and discharge.

**Feasibility and acceptability:** 99% of participants completed daily sessions of CBM-I. Attrition rate for the discharge assessment was low (11%), typically due to inpatient hospitalization or an

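### Under a conventional two-sided 5% unadjusted comparison, 200 recruited with 15% dropout gives about 74% power, not the stated >80%, and the 4-per-month recruitment benchmark carries the same gap

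*SAP*

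**What the plan says.** The power paragraph is in SAP section VI, under Phase 2: Open Trial. One stated goal of the project is to measure the recruitment rate at the site and "to compare it to the rate needed for an adequately powered RCT". That rate is given as "4 individuals per month = 200 participants over 50 months".

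The target effect is d = 0.40, equated with a "post-treatment between-group difference of 2.8 points on the WSAS". The calculation is said to use these figures together with 15% dropout taken from pilot work, and it ends: "We estimated that a sample size of 200 would give us >80% power to detect a group difference".

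The paragraph gives no significance level, sidedness, test, covariate adjustment or allocation ratio. It does not say whether 200 is counted before or after dropout, although the recruitment equation treats it as the number recruited.

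**The concern.** Two hundred participants, split equally, is almost exactly the number of completers needed to detect d = 0.40 with 80% power at two-sided 5%. If 15% are then lost, the power cannot still exceed 80% under that test. The paragraph states the loss, but its result looks like the figure without it.

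The 4-per-month benchmark is simply 200 divided by 50, so it inherits any shortfall. A site recruiting, say, 4.2 per month would be judged able to support an adequately powered trial when, under the conventional analysis, it would fall short. Judging that kind of feasibility is a stated purpose of this pilot.

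**Working it through.** **Inputs from the SAP power paragraph:** d = 0.40; 2.8 WSAS points, so the implied SD is 2.8 / 0.40 = 7.0; 200 recruited over 50 months; 15% dropout; claimed power >80%.

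**Assumptions not in the documents:** alpha 0.05 two-sided, unadjusted two-sample t-test, 1:1 allocation. Equal allocation is the choice most favourable to the plan.

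**Formula.** With n analysed per arm, the test statistic follows a non-central t distribution with 2n − 2 degrees of freedom and non-centrality d × √(n/2). Power is the probability that it falls beyond the two-sided critical value.

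**Reproducing the stated figure.** With n = 100 (no loss), non-centrality = 0.40 × √50 = 2.828 and the critical value is 1.972. Power = 80.4%, which matches the claim.

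**Applying the stated dropout.** 200 × 0.85 = 170, so n = 85. Non-centrality = 0.40 × √42.5 = 2.608 and the critical value is 1.974. Power = 73.7% (normal approximation 74.1%; simulation with 100,000 runs 73.6%).

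| Loss | Analysed | Per arm | Power |
|---|---|---|---|
| 0% | 200 | 100 | 80.4% |
| 1% | 198 | 99 | 79.97% |
| 11% | 178 | 89 | 75.6% |
| 15% | 170 | 85 | 73.7% |

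The 11% row uses the discharge attrition that the Protocol reports for the pilot RCT. It is a sensitivity check, not the SAP's input.

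**Number needed.** Power of 80% requires 99.08 per arm, or 198.2 in total, so a recruited sample of 200 tolerates a loss of only (200 − 198.2) / 200 = 0.9%. Allowing for 15% dropout:

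- 198.2 / 0.85 = 233.1; with whole, equal arms of 100, 200 / 0.85 = 235.3, rounded up to 236.
- Rate over 50 months: 233.1 / 50 = 4.66 to 236 / 50 = 4.72 per month.
- Duration at 4 per month: 233.1 / 4 = 58.3 to 236 / 4 = 59.0 months.

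**Detectable effect with 170 analysed.** At 80% power, d = 0.432, which is 0.432 × 7.0 = 3.0 WSAS points against the stated 2.8.

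**Analyses that could support >80% with 85 per arm** (none is stated in the SAP):

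- One-sided 5%: 83.0%.
- Two-sided with baseline adjustment, where the effective d is 0.40 / √(1 − r²) and r is the baseline–outcome correlation: r = 0.30 gives 77.6%, r = 0.38 gives 80.0%, r = 0.50 gives 84.9%. The smallest r that reaches 80% is about 0.38.
- Two-sided on the mean of three post-baseline visits, assuming d = 0.40 at each visit and a common within-person correlation ρ. The variance factor is (1 + 2ρ)/3, and power is about 89%, 86% and 83% for ρ of 0.5, 0.6 and 0.7.

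**The case against.** The strongest reply is that no arithmetic error has been demonstrated. The alpha, the sidedness, the test and the allocation behind 73.7% were all supplied by the reader. With dropout applied, ordinary choices do exceed 80%: a one-sided test, baseline adjustment with a moderate correlation, or a longitudinal analysis. The hypothesis is worded directionally, and the present trial's schedule of assessments includes the WSAS at baseline, so a covariate would be available if the later trial used the same schedule.

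The reply also points to small consequences. The calculation is labelled preliminary and serves a trial not yet proposed. The recruitment comparison has no decision rule and does not appear in the SAP's table of target outcomes.

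Part of this stands. The stated power is not wrong under every possible analysis, and the inference that dropout was left out remains an inference. But a superiority hypothesis does not imply a one-sided test, and the SAP describes only a difference between groups after treatment, with no covariate and no averaging over visits. A reader cannot verify >80% from what is written, and the default reading contradicts it. The limited consequence bears on severity, not on whether the text needs correcting.

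**Conclusion.** The concern holds under the condition it states. For a two-sided 5%, unadjusted, 1:1 comparison at d = 0.40, 200 recruited with 15% dropout gives 73.7% power, about 7 percentage points below the 80.4% obtained with no loss. The 4-per-month benchmark is about 15% below the roughly 4.7 per month needed for 80% power.

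Under this convention, either meaning of 200 leaves something to correct. If it is the number recruited, power is about 74%; if it is the number analysed, about 236 must be recruited.

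Confidence is high that >80% does not reproduce under the conventional analysis. It is moderate that dropout was not applied, because the alpha, sidedness and model are not given. This should be fixed, but its reach is limited to planning the later RCT. The present randomised phase plans effect sizes with 95% confidence intervals and does not depend on this calculation.

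**What to change.** In the SAP power paragraph, state the alpha, sidedness, analysis model and allocation ratio, and say whether 200 means recruited or analysed. Then take one of three routes:

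1. Keep 200 recruited and 15% dropout, and restate the power as about 74% under the conventional test.
2. Keep 80% power and raise the benchmark to about 233 to 236 recruited: about 4.7 per month over 50 months, or about 59 months at 4 per month.
3. If a one-sided, baseline-adjusted or repeated-measures analysis was intended, say so and give the alpha and the assumed correlation that deliver >80% with 170 analysed.

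The cost is one or two sentences. Under routes 1 and 2 the stated power or the benchmark becomes somewhat less favourable. Nothing changes in this trial's enrolment or analysis.
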